#### HIV Testing and Counselling (Y-Check 2 in the community hubs only)

All participants will be offered standard provider-initiated HIV testing and counselling (PITC) using national guidelines. Clients will be offered a self-test for HIV on-site using an oral mucosal test (OMT). The staff member will provide a demonstration on the use of the OMT. All positive HIV test results will require a second confirmatory test with a blood-based rapid diagnostic test (RDT). Discordant or

inconclusive results will be further evaluated according to national guidelines. For 16-19 year olds who test positive, the counsellor/nurse will suggest that the adolescents' trusted adult be contacted so that they can join the discussion of the results and next steps. The study team will facilitate referral of those who test positive to a local health facility to register for HIV care. HIV+ adolescents will be encouraged to join adherence support groups run by local NGOs/CBOs. If HIV positive and sexually active, adolescents will be asked to refer their partners to government health clinics for HIV testing.

Sexual and reproductive health (Y-Check 2 in the community hubs only)

- All participants will be offered male condoms regardless of reported levels of risk behaviour.
  Those reporting high risk sexual behaviour (sexual intercourse without a condom, multiple sexual partners) in the pre-consultation questionnaire will be offered risk-reduction counselling.
- HIV pre-exposure prophylaxis (PrEP), which confers significant protection against HIV acquisition, is being rolled-out in Zimbabwe for populations at high risk of HIV acquisition including men who have sex with men and girls aged 15-24 years who report high risk sexual behaviours. Participants who report high risk sexual behaviour and who test negative for HIV will be referred to a local health facility to assess their eligibility to receive PrEP according to national guidelines.
- Participants will be offered screening tests for sexually transmitted infections (STIs). Urine samples will be screened for infection with Gonorrhea (GC) and Chlamydia Trachomatis (CT) using the closed GeneXpert system. This is a near point of care test which provides results in 90 minutes. Females will also take their own vaginal swabs which will be tested for trichomonas vaginalis (TV) using a point of care lateral flow assay. There will be a private space available for girls to self-administer the vaginal swabs. This will either be in a bathroom or a private room they can access on their own. They will be provided gowns and drapes should they wish to use these. They will place the swab into a container and return the container to Y-Check staff after leaving the private space.

Syndromic management and treatment of STIs will be provided according to national guidelines. Participants who test positive for an STI and who had not already been treated following syndromic management will be followed up and treated according to national guidelines. Partner notification slips will be provided to those who are treated for STIs.

• For females, **Pregnancy testing and contraception** (emergency contraception, Depo injections and the oral contraceptive pill) will be provided upon request and participants will be referred to the local health facility for longer-term contraception care.

# Menstrual health and hygiene (MHH)

Females will receive guidance on MHH including advice on pain management along with the provision of a choice of reusable MHH products (e.g. reusable pads, reusable period underwear) and analgesia.

#### Immunisation

The Human Papillomavirus vaccine was introduced for adolescents in 2018 targeting Grade 5 learners (age 10-14 y) or out of schoolgirls aged 10y. Participants will be asked to show their immunisation

record (when available) or verbally report whether they have had the HPV vaccination. Where vaccination cards show that the participant has not completed the recommended schedule, the nurse will either link the girls to the National HPV programme or provide the first dose of the vaccine and refer for subsequent doses, if necessary. Eye health

Visual acuity problems will be identified using the Peek Acuity smartphone app.The Snellen Tumbling-E card will be available as a back-up screening tool. Those who are identified as having problems with their distance vision (worse than or equal to 6/12 in either eye)) will be referred to specialist services for further examination and to identify the cause of sub-optimal acuity. Treatments such as eye drops and and glasses will be provided free of charge by the Y-Check programme. Participants with visual impairment will be given a printout of a smartphone simulation of what they are able to see vs. what someone with normal vision would see with the referral letter to present to their parent or guardian.

#### Hearing

Hearing problems will be identified using the HearScreen or HearWHO smartphone app. Participants who fail the HearScreen or HearWHO test may have the threshold of their hearing loss measured using HearTest and the nurse will check for the presence of wax using an otoscope or the smartphone app. If wax is present, then the nurse will attempt to remove the wax and then repeat the hearing test. For those who still fail the hearing test and/or where wax was not present, the participant will be referred to specialist services for further examination and potential treatment with antibiotics for chronic middle ear infection, wax removal, or hearing aid fitting.

#### Physical impairment

We will include questions from The Washington Group/UNICEF Child Functioning Module child screening tool in the pre-consultation questionnaire to identify adolescents who might have a physical impairment. All adolescents will be asked to undergo a short non-invasive test for lower limb impairment such as a jump or squat test. Upper limb impairment and fine motor skills will be assessed using existing tools e.g. grip strength test, functional reach test, or through the development of new context specific tools. Adolescents with significant untreated physical impairment will be referred to a physiotherapist.

#### **Epilepsy**

We will screen adolescents for convulsive seizures using questions adapted from existing tools.  There is limited epidemiological data on epilepsy in the African Region and the prevalence is estimated to be anything from 2.2 to 58 per 1000 with the second highest incidence in the age group 10-19 years.  Participants who screen positive will be referred for diagnosis, counselling and treatment. 

#### Blood pressure (Y-Check 2)

The blood pressure of participants will be measured using a digital sphygmomanometer. Two or three measurements will be taken at set intervals during the check-up visit. Participants with suspected prehypertension will receive counselling to identify modifiable risk factors e.g. obesity, lack of physical exercise, smoking, and will be advised to attend a health facility to repeat their BP measurement after 6 months. Those with suspected hypertension will be given advice on diet and exercise and referred to the local health facility for further assessment. 

#### **Schistosomiasis**

A national study of schistosomiasis in Zimbabwe published in 2014 showed a prevalence of 5.2%

(95%CI 2.9,8.6%) for the combination of S. haematobium and S. mansoni in primary schools in Chitungwiza and of 9.6% (95%CI 8.0,11.5%) in Harare (Midzi et al., 2014). In Chitungwiza, the estimated prevalence of S. haematobium was almost 10 times higher than that of S. mansoni. We will therefore test initially only for S. haematobium using a urine filtration lab test to detect the parasites in the urine. Considered the 'gold' standard, this test shows high sensitivity and specificity. We will review the screening procedure after the first 200 adolescents have been screened. If the prevalence of S. haematobium is 15% or higher (n=200 will allow 5% margin of error on prevalence estimate) then we will additionally test urine samples for S. mansoni using the commercially available urine-based Point of Care test, based on detection of circulating cathodic antigen (CCA). In this situation, the initial 200 adolescents will be revisited so that they can also be tested for S. mansoni. Detection of schistosomiasis will require collecting urine specimens which will be tested in the lab or on-site as stated above. National protocols for treatment will be provided as needed for those who test positive."

#### 3.7.3 Configuration of Services

[figure not shown]
On the first day of the screening visit, the intervention team will arrive at the school or community location and set up the intervention room/tent. Clients at school settings (Y-Check 1 and 2) will provide written assent and provide completed parental consent forms before proceeding through the check-up visit stations. Clients at community settings (Y-Check 2) will provide verbal consent before proceeding through the check-up visit stations.

Y-Check will be configured to be "youth-friendly" i.e. able to effectively attract adolescents, meet their needs comfortably, and responsively and retain them in care. Visual and auditory privacy will be prioritised, services will be appropriate and affordable, staff will have received training in youth-friendly service delivery, and adolescents will be involved in the design of the intervention content and delivery (see section 4.2.1). Visits will involve a five staged-process, consisting of: i) registration; ii) completion of a screening questionnaire; iii) a physical examination; iv) laboratory tests; and v) a review with a nurse.

#### **STATION 1: Registration**

During registration, a trained research assistant will welcome adolescents, record their date of birth and sex, and national ID number. Research cohort participants will also be provided with a personal identifying number (PID). They will also record their ID numbers, name, address and mobile phone numbers on a separate locator log. While clients are waiting to proceed to the next station they will have access to health and well-being information (see section 3.6.1).

Figure 4. Y-Check configuration of services

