#### 3.7.1 Information, education and communication (IEC)

During check-up visits in all settings, IEC materials about mental health, diet and exercise, oral health, drugs and alcohol, sexual and reproductive health (SRH), HIV, safety, and general health will be available in the form of video clips, games, information leaflets and social media postings. IEC materials will be appropriate for various age and literacy levels. Materials will also be provided to help adolescents to navigate the health system and find a trusted provider if they have an urgent issue. The Y-Check team will provide details on how clients can get tailored advice or further information from the Y-Check team following the check-up visit, for example, if they can't access the trusted provider. The format of this support will be designed with young people during Phase 1 and may take the form of a live chat option on a Y-Check webpage, a phone number that can be messaged (via SMS or WhatsApp), or a hotline phone number that can be called free of charge. All IEC materials to be shared in schools will be submitted to the Curriculum Development and Technical Services Department for confirmation of curriculum alignment.

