#### **STATION 2: Pre-consultation screening questionnaire**

The adolescent client will then be given an audio computer-assisted self-interviewing (ACASI) questionnaire on a tablet computer and respond to questions on home environment, education and employment, social activities, physical activity, diet, mental health, alcohol, tobacco and drug use, sexual health, male circumcision, oral health, adolescent immunisation history, and general health questions (see Section 3.6.2). The questionnaire, developed and validated during Phase 1, will be based on the WHO Global School-based Student Health Survey tool, HEEADSSS and other existing previsit screening tools for adolescents. The research assistant will assist with any challenges or questions during completion of the questionnaire or when using other tablet features. Completion of all sections of the questionnaire will be incentivised by a rewards system e.g. where clients get to customise their electronic avatar on the tablet as they proceed through the questionnaire or gather points that can be used to retrieve health and well-being products at the end e.g. soap, extra sanitary pads, deodorant etc. Incentives will be decided on in collaboration with adolescents and other stakeholders during Phase 1. In case of technical difficulties, a paper and pen back-up questionnaire will be available. If a client does not want or is unable to self-complete the questionnaire, then a member of staff will interview them and complete the questionnaire.

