#### 4.3.1 Cohort recruitment and follow-up

Prior to the Y-Check visit, programme participants will be invited to join the research cohort and agree to the following additional activities:

- Self-completion of an additional module of the pre-consultation questionnaire (to measure baseline outcomes not captured for programme participants e.g. knowledge, intention, agency, educational outcomes)
- Observation of check-up visit and referral visit procedures by a Y-Check team member.
- Exit interviews
- Follow up visits at 4-months and 12-months (questionnaire and screening tests)
- Potential participation in qualitative interviews or group activities

Y-Check 1: The information sheet distributed by the school about the check-up visits (section 3.7) will include information about the Y-Check research cohort and the need for separate consent to participate in the research study. Eligible students will be asked to return completed informed parental consent and individual assent forms either before or on the day of the check-up visit.

Eligibility criteria will be:

- Currently enrolled in Grade 5, 6 or 7 in one of the study primary schools
- Adolescent and their parent/guardian have consented/assented to participate in the check-up visit
- Written informed parental/guardian consent and client assent to participate in the research study

Y-Check 2: The information sheet distributed by the school about the check-up visits (section 3.7) will include information about the Y-Check research cohort and the need for separate consent to participate in the research study. Eligible students will be asked to return their completed informed consent form either before or on the day of the check-up visit.

In the community, mobilisation and advertisement will encourage adolescents to attend the community hubs for check-up visits and will describe the accompanying research study. At the community hubs,

following confirmation of eligibility, clients will be asked to provide written informed consent to participate in the research study.

Eligibility criteria will be:

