Following the initial check-up screening visit, and during 4-month and 12-month follow-up visits, clients will be asked to self-complete a tablet questionnaire, and undergo clinical screening tests. The content of the follow-up visits will be decided on during Phase 1 following piloting and costing of the screening and referral protocols for each condition. The follow-up visits may offer a reduced number of clinical screening tests.

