#### 7.4 Risk-benefit assessment

The risks and benefits of the Y-Check intervention will be described to participants and their parents/guardians during the consent process. Y-Check participants will benefit from early detection of health problems, health promotion, and the development of health-seeking behaviours. Those who choose to participate can opt out of responding to questions or completing examinations/procedures. HIV and STIs are conditions, which are associated with stigma and anxiety. The Y-Check team will provide counselling to those participants testing positive for HIV or STIs. There is also a risk of negative consequences of a parent or guardian finding out that an adolescent has a drug or alcohol problem. However, if needed, participants and their parents or guardian will have access to on-the-spot initial Y-Check counselling services and assisted referral to longer-term services. The protocols and procedures for communicating with adolescents and their families will be carefully developed in collaboration with the YAG and community stakeholders.

As for any health care, the tests and treatment provided can have side-effects that can be serious or minor. The tests could cause anxiety. The blood test could cause discomfort or a small bruise, as with any other blood test. While the possibility of this happening is low, the informed consent and assent forms will specify these risks clearly to make sure that participants are aware of the possibility. In the unlikely case of an adverse event, the team will be trained to provide care and support, as well as notify the relevant school authorities (for those seen in schools). If urgent care is required, they will be supported to attend a local health facility.

Risks will be minimized by explaining the procedures in detail to adolescents during the school sessions, as well as during the process of obtaining informed consent in schools and community venues. Staff will be trained to detect adverse events and a protocol will be in place to ensure action in the rare case that such an event occurs.

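### The written visit order lets clients see health-education materials before the baseline for knowledge, intention and agency is taken, and class-session timing relative to that baseline is not fixed

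*Protocol*

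**What the plan says.** Section 3.7.3 of the protocol fixes the order of the visit: "Visits will involve a five staged-process, consisting of: i) registration; ii) completion of a screening questionnaire; iii) a physical examination". At Station 1, "While clients are waiting to proceed to the next station they will have access to health and well-being information (see section 3.6.1". No section 3.6.1 exists, and the reference evidently means section 3.7.1, which describes the information, education and communication (IEC) materials. Station 2 follows: "The adolescent client will then be given an audio computer-assisted self-interviewing (ACASI) questionnaire on a tablet computer". The text of Figure 1 has the same order, with registration and health information listed ahead of the pre-consultation questionnaire.

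Section 3.7.1 gives the content: "During check-up visits in all settings, IEC materials about mental health, diet and exercise, oral health, drugs and alcohol", followed by sexual and reproductive health, HIV, safety and general health, as videos, games, leaflets and social media posts. It adds: "Materials will also be provided to help adolescents to navigate the health system and find a trusted provider".

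Section 4.3.1 says that cohort members complete an extra module of the pre-consultation questionnaire "to measure baseline outcomes not captured for programme participants e.g. knowledge, intention, agency, educational outcomes".

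In schools the programme also includes whole-class education sessions (sections 3 and 3.6). Section 3.4 leaves their timing to be agreed with the principals. Section 7.4 says: "Risks will be minimized by explaining the procedures in detail to adolescents during the school sessions".

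Objective 2(iii) in section 2.2 is to estimate short-term impact on outcomes that include knowledge, intentions and agency. Section 6.1 lists knowledge and agency as secondary client outcomes. Section 6.3 analyses outcomes measured at two or more time-points by a before-after comparison.

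**The concern.** A before-after estimate measures the programme's effect only if the first measurement comes before the programme. Here the first measurement of knowledge, intention and agency can follow contact with materials on the same subjects, including how to use health services.

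The absence of a control arm makes this matter more. Section 2.3 defends the uncontrolled design partly on the ground that undiagnosed chronic conditions provide their own counterfactual. That argument does not extend to knowledge, intention or agency. For these, the Station 2 module is the only comparator. Uplift already present at that point is counted as baseline, and the programme gets no credit for it.

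The defect lies in field procedure, so an analysis plan cannot repair it. Once the module has been completed after exposure, that participant's pre-programme value is gone.

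**Working it through.** The plan states no figure for these outcomes, so there is none to reproduce. The check is of sequence, followed by an illustration.

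**Sequence in all settings**

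1. Registration is first and the questionnaire second (section 3.7.3).
2. Access to health information is given between the two (Station 1). Section 3.7.1 applies it to every setting, so community hubs are included.
3. The baseline module is part of the second step (section 4.3.1).
4. No section requires the module to be completed before the materials are opened.

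Followed as written, steps 1 to 3 allow exposure before baseline.

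**Sequence in schools**

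1. The class sessions are a programme component (section 3) on overlapping topics: nutrition, exercise, mental health, substance use and sexual health (section 3.6).
2. Their date relative to the check-up is open (section 3.4).
3. Section 7.4 has procedures explained in school sessions as a way to reduce risk. That makes sense only if those sessions come before the procedures. It does not say that they are the education sessions of section 3.6.

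The timing is therefore unfixed, with a hint that sessions may come first.

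**Overlap with the outcome**

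Section 6.1 measures knowledge about health services and health behaviours. Section 3.7.1 teaches health behaviours and how to find services. The match is direct for knowledge and looser for intention and agency.

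**Illustration of size (assumed inputs, none from the protocol)**

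Let g be the true gain from the pre-programme state to follow-up, a the uplift already present when the module is completed, and s = a/g. Then

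observed change = g − a = g × (1 − s).

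| True gain g (points) | s = 0 | s = 10% | s = 25% | s = 50% |
|---|---|---|---|---|
| 10 | 10 × 1.00 = 10 | 10 × 0.90 = 9 | 10 × 0.75 = 7.5 | 10 × 0.50 = 5 |
| 20 | 20 × 1.00 = 20 | 20 × 0.90 = 18 | 20 × 0.75 = 15 | 20 × 0.50 = 10 |

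If a is positive, the observed change is smaller than g. The table shows how the bias works. It does not estimate the bias in this study.

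**The case against.** The strongest reply is that the exposure may be slight. Station 1 offers access while waiting, in a visit that Figure 1 puts at 30 to 60 minutes. Some clients will look at nothing, the materials remain available through the visit, and the nurse's guidance comes after the baseline. This stands: the loss from the waiting area alone could be close to zero. It also rules out saying that participants have already received the education.

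A reader might infer more from the documents, but they do not support it:

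- **That class sessions come before the visit.** Section 7.4 suggests this, but section 3.4 leaves the timing open. Only unfixed timing is established.
- **That section 4.3.2 moves the baseline to after the visit.** It says: "Following the initial check-up screening visit, and during 4-month and 12-month follow-up visits, clients will be asked to self-complete a tablet questionnaire". Section 4.3.1 assigns the baseline to the pre-consultation module and lists exit interviews separately. Section 6.1 separates the same sources, and section 4.3.3 collects uptake and acceptability data after the visit. The natural reading is the exit interview.
- **That school and hub results, or results between schools, become incomparable.** Section 6.3 presents the primary outcome and single-time-point outcomes by four age-sex groups. It plans no school-versus-hub or between-school comparison of these outcomes.
- **That a known share of the effect is lost.** Any percentage is an assumption.

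It can also be said that procedures are refined in the pilot (section 4.2.4) and that the digital platform will log information viewed (section 5.3, Table 3). Refinement is possible, but the current text does not ask for it. Platform logs would not cover leaflets or class sessions, and they cannot recover the value before exposure.

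Finally, a bias towards no change would not create a false benefit. That is right, and it limits the seriousness. It still weakens the estimate that objective 2(iii) sets out to obtain.

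**Conclusion.** The point holds as one of sequencing. As written, IEC materials are available before the module that supplies the baseline for knowledge, intention and agency, and the timing of class sessions relative to that module is not fixed. Gain made before the module is omitted from an uncontrolled before-after estimate, which this mechanism biases towards no change.

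The direction rests on one assumption, that exposure raises scores. The size cannot be derived from the protocol. The consequence is confined to objective 2(iii) and the client outcomes carried by the module, most directly knowledge. The primary outcome (care or referral completed within 4 months) and the clinical screening results do not depend on this baseline and are not affected. The change is worth making because it is cheap and because the lost baseline cannot be restored later.

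**What to change.** In sections 3.7.3 and 4.3.1, require the research baseline module to be completed before any access to IEC materials. Either of two routes would do:

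- open access to the materials only after Station 2; or
- give the module at consent or assent. Section 4.3.1 already invites cohort members before the visit, and school forms may be returned before the day. At the hubs, where consent is given on site, the module would follow consent directly.

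In schools, give the module before the whole-class sessions where the agreed timetable allows. Where it does not, record each participant's prior session exposure and state that the before-after estimate excludes its effect. Requiring every school to hold its sessions after the check-up weeks is more than is needed. It would override the timing agreed with principals and could alter the intervention, since Figure 1 sets the sessions alongside a supportive environment for service uptake.

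The cost is small: clients wait at Station 1 without the materials, or the module needs a slightly earlier contact.
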